16.1 Appendix 1: Clinically notable laboratory values and vital signs

Central laboratory assessments:

The central laboratory will flag on the central laboratory report

- i) all values falling outside of the central laboratory normal ranges
- ii) all values falling in the below alert range:
 - a. Hemoglobin levels < 8 g/dL (< 5 mmol/L)
 - b. Total leukocyte count $< 2,000/\mu L (2 \times 10^{9}/L)$
 - c. Platelets $< 50,000/\mu L (50 \times 10^9/L)$
 - d. Neutrophil count < 1,000/ μ L (1 x 10⁹/L)

Vital signs:

Clinically notable values for vital signs are defined as:

- heart rate of < 50 and > 100 bpm
- systolic blood pressure of < 90 and ≥ 140 mmHg
- diastolic blood pressure of < 60 and ≥ 90 mmHg

The investigator will report an adverse event for clinically significant vital-sign or laboratory abnormalities.

16.2 Appendix 2: Liver event and laboratory trigger definitions & follow-up requirements

Confidential

	Definition/ threshold
Liver laboratory triggers	 ALT or AST > 5 × ULN
If ALT, AST and total bilirubin normal at baseline:	 ALP > 2 × ULN (in the absence of known bone pathology)
	 Total bilirubin > 3 × ULN (in the absence of known Gilbert syndrome)
	 ALT or AST > 3 × ULN and INR > 1.5
	 Potential Hy's Law cases (defined as ALT or AST > 3 × ULN and Total bilirubin > 2 × ULN [mainly conjugated fraction] without notable increase in ALP to > 2 × ULN)
	 Any clinical event of jaundice (or equivalent term)
	 ALT or AST > 3 × ULN accompanied by (general) malaise, fatigue, abdominal pain, nausea, or vomiting, or rash with eosinophilia
	Any adverse event potentially indicative of a liver toxicity
If ALT or AST abnormal at baseline:	 ALT or AST > 3x baseline or > 300 U/L (whichever occurs first)

Table 16-1 Liver event and laboratory trigger definitions

Table 16-2	6-2 Follow up requirements for liver laboratory triggers - ALT, AST, TBL			
	ALT	TBL	Liver Symptoms	Action
ALT increase w	vithout bilirubin increa	se:		
	If normal at baseline: ALT > 3 x ULN If elevated at baseline: ALT > 2 x baseline or > 300 U/L (whichever occurs first)	Normal For participants with Gilbert's syndrome: No change in baseline TBL	None	 No change to study treatment Measure ALT, AST, ALP, GGT, TBIL, INR, albumin, CK, and GLDH in 48-72 hours. Follow-up for symptoms.
	If normal at baseline: ALT > 5 x ULN for more than two weeks If elevated at baseline: ALT > 3 x baseline or > 300 U/L (whichever occurs first) for more than two weeks	Normal For participants with Gilbert's syndrome: No change in baseline TBL	None	 Interrupt study drug Measure ALT, AST, ALP, GGT, TBIL, INR, albumin, CK, and GLDH in 48-72 hours.
	If normal at baseline: ALT > 8 x ULN	Normal	None	Follow-up for symptoms.Initiate close
ALT increase w	vith bilirubin increase:			monitoring and workup
	If normal at baseline: ALT > 3 x ULN If elevated at baseline: ALT > 2 x baseline or > 300 U/L (whichever occurs first)	TBL > 2 x ULN (or INR > 1.5) For participants with Gilbert's syndrome: Doubling of direct bilirubin	None	 for competing etiologies. Study drug can be restarted only if another etiology is identified and liver enzymes return to
	If normal at baseline: ALT > 3 x ULN If elevated at baseline:	Normal or elevated	Severe fatigue, nausea, vomiting, right upper quadrant pain	baseline.

Table 16-2 Follow up requirements for liver laboratory triggers - ALT, AST, TBL

ALT	TBL	Liver Symptoms	Action
ALT > 2 baseline			
or > 300 (whiche occurs f	/er		

Table 16-3Follow up requirements for liver laboratory triggers - Isolated
Hyperbilirubinemia

Criteria	Actions required	Follow-up monitoring
Total Bilirubin (isolated)		
>1.5 – 3.0 ULN	 Maintain treatment Repeat LFTs within 48-72 hours 	Monitor LFTs weekly until resolution to ≤ Grade 1 or to baseline
> 3 - 10 × ULN (in the absence of known Gilbert syndrome)	 Interrupt treatment Repeat LFT within 48-72 hours Hospitalize if clinically appropriate 	Monitor LFTs weekly until resolution to ≤ Grade 1 or to baseline (ALT, AST, total bilirubin, Alb, PT/INR, ALP and GGT)
	 Establish causality Record the AE and contributing factors (e.g. conmeds, med hx, lab) in the appropriate CRF 	Test for hemolysis (e.g. reticulocytes, haptoglobin, unconjugated [indirect] bilirubin)
> 10 x ULN	 Discontinue the study treatment immediately Hospitalize the participant Establish causality Record the AE and contributing factors(e.g. conmeds, med hx, lab)in the appropriate CRF 	ALT, AST, total bilirubin, Alb, PT/INR, ALP and GGT until resolution (frequency at investigator discretion)
Any AE potentially indicative of a liver toxicity	 Consider study treatment interruption or discontinuation Hospitalization if clinically appropriate Establish causality Record the AE and contributing factors(e.g., conmeds, med hx, lab) in the appropriate CRF 	Investigator's discretion

Based on investigator's discretion investigation(s) for contributing factors for the liver event can include: Serology tests, imaging and pathology assessments, hepatologist's consultancy; obtaining more detailed history of symptoms and prior or concurrent diseases, history of concomitant drug use, exclusion of underlying liver disease.

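### Table 16-2 has no automatic interruption or restart rule for two Table 16-1 liver events when AST, not ALT, is the raised enzyme

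*Protocol*

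**What the plan says.** Table 16-1 (Protocol Section 16.2) lists the laboratory findings that count as liver events. Two of them combine a transaminase with a sign of impaired liver function, and in both either enzyme is enough. The potential Hy's law case is "defined as ALT or AST > 3 × ULN and Total bilirubin > 2 × ULN", with bilirubin mainly conjugated and no notable rise in ALP. The other is "ALT or AST > 3 × ULN and INR > 1.5".

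Section 9.1.1 sends liver events to Section 16.2 for the rule on stopping study treatment. There, Table 16-2 is titled "Follow up requirements for liver laboratory triggers - ALT, AST, TBL". Its columns are ALT, TBL, liver symptoms and action. Its combined row pairs an ALT limit with "TBL > 2 x ULN (or INR > 1.5)". That limit is 3 × ULN for a normal baseline, or "ALT > 2 x baseline or > 300 U/L (whichever occurs first)" for an elevated one. The action is to interrupt the drug, and the restart condition is strict: "Study drug can be restarted only if another etiology is identified", and enzymes must also have returned to baseline. In the body of the table AST appears only in the list of tests to repeat.

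Table 16-3 covers isolated hyperbilirubinemia. Its last row, "Any AE potentially indicative of a liver toxicity", carries the action "Consider study treatment interruption or discontinuation". Section 10.2.1 applies to every Table 16-1 event. It requires repeat tests, close observation and a causality assessment, but leaves interruption and discontinuation to what is deemed appropriate.

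**The concern.** The sponsor defines one signal on either enzyme and then writes the stop rule on only one of them. For two of the most serious laboratory triggers in Table 16-1, a required interruption and a defined restart condition therefore depend on which transaminase rose. The title of Table 16-2 names AST, so a site would expect to find an AST rule there and would not.

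The participant-level rule carries some weight in this trial. Section 3 says that MHV370 is being given to SjS and MCTD patients for the first time. Section 10.3 provides for no committee. The study stopping rules in Section 9.3 contain no liver-specific criterion. A site that finds no row in Table 16-2 and turns to Table 16-3 with bilirubin between 2 and 3 × ULN would read an instruction to maintain treatment, the opposite of what the ALT row requires.

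**Working it through.** The plan gives no figure to reproduce here. The check runs mirrored cases through the tables. Values are multiples of ULN, so no laboratory limit has to be assumed (INR is as measured).

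**Assumptions.** ALT, AST and bilirubin are normal at baseline, ALP is not above 2 × ULN, bilirubin is mainly conjugated, and there are no liver symptoms and no Gilbert's syndrome. The interrupt action in Table 16-2 is read as one cell running over rows 2 to 5 below, as the layout suggests.

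**Step 1: Table 16-2 limits for a normal baseline.**
1. ALT > 3, bilirubin normal, no symptoms: no change, retest.
2. ALT > 5 for more than two weeks, bilirubin normal: interrupt.
3. ALT > 8, bilirubin normal: interrupt.
4. ALT > 3 with TBL > 2 or INR > 1.5: interrupt.
5. ALT > 3 with liver symptoms: interrupt.

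The lowest enzyme limit is ALT > 3. A participant with ALT at or below 3 × ULN meets no row, whatever the AST.

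**Step 2: mirrored cases.**

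| Case | ALT | AST | TBL | INR | Table 16-1 | Table 16-2 |
|---|---|---|---|---|---|---|
| A, on ALT | 3.5 | 2.5 | 2.5 | 1.0 | potential Hy's law | interrupt (row 4) |
| A, on AST | 2.5 | 3.5 | 2.5 | 1.0 | potential Hy's law | no row |
| B, on ALT | 3.5 | 2.5 | 1.0 | 1.6 | INR trigger | interrupt (row 4) |
| B, on AST | 2.5 | 3.5 | 1.0 | 1.6 | INR trigger | no row |
| C, on AST | 2.75 | 9.0 | 2.9 | normal | potential Hy's law, and AST > 5 | no row |

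Within A and within B the Table 16-1 event is the same and only the enzyme differs. Case C shows that the height of AST does not matter: 2.75 < 3, so 0 of 5 rows apply.

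**Step 3: can Table 16-3 fill the gap?** By its terms it covers isolated bilirubin rises, which a case with AST above 3 × ULN is not. If a site applies it anyway:
- TBL > 3 to 10 × ULN: interrupt. TBL > 10 × ULN: discontinue. A case with ALT 2.5, AST 3.5 and TBL 3.5 would then be interrupted.
- TBL > 1.5 to 3 × ULN: maintain treatment. Cases A (on AST) and C stay uncovered.
- TBL normal: no row. Case B (on AST) stays uncovered.

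On this generous reading the remaining gap is TBL above 2 and up to 3 × ULN, or INR above 1.5 with TBL at most 3 × ULN.

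**Step 4: with AST added to row 4.** A and B on AST meet it (3.5 > 3 with TBL 2.5 > 2, and 3.5 > 3 with INR 1.6 > 1.5). So does C (9.0 > 3 with TBL 2.9 > 2). All three then require interruption.

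**The case against.** The strongest reply is that an AST-driven case is not left unmanaged. Section 9.1.1 makes discontinuation mandatory once the investigator believes that continuing would harm the participant, or judges that it might pose a safety risk. An AST-driven potential Hy's law case could well meet that bar. Section 10.2.1 follow-up applies in full, and Section 6.7.2 adds a prompt to consider stopping for a suspected SAE. Section 9.1.1 also cites a hepatotoxicity guideline that may contain an AST rule. All of this stands. A reader might infer that drug would have to continue in an AST-driven case, and the documents do not support that. What they lack is an automatic threshold and a restart condition.

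A reader might also infer from Section 6.6, which allows interruption only for confirmed SARS-CoV-2 infection, that interruption is specifically barred for AST. That does not follow. Section 6.6 conflicts equally with the ALT interrupt rows, with Table 16-3 and with the renal rules in Section 16.3, and it does not limit discontinuation. It is a separate drafting conflict and adds no weight here.

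ALT-only action may be deliberate, because AST can come from muscle and myositis is one of the diagnostic signs of MCTD. This is a good reason to leave the enzyme-only and symptom rows on ALT, the latter also because fatigue is so common in SjS. It is weaker for the combined row. Muscle injury alone would not explain raised bilirubin or INR, and Table 6-3 prohibits anticoagulants. The sponsor itself chose either enzyme for these two triggers in Table 16-1.

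Finally, Table 16-2 was never a one-to-one map of Table 16-1. ALP above 2 × ULN, for example, has no action row of its own. That limits what may be claimed for the fix but does not remove the mismatch.

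**Conclusion.** The point holds within these limits. In the documents available, two Table 16-1 events have no automatic interruption or restart rule when AST is the raised enzyme and ALT is at or below 3 × ULN (normal baseline): AST > 3 × ULN with TBL > 2 × ULN, and AST > 3 × ULN with INR > 1.5. The same signals on ALT have both. For AST, stopping depends on the investigator's judgement.

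The gap covers all such cases if Table 16-3 is kept to isolated bilirubin rises, and the narrower range in Step 3 of the working if it is not. The cases are constructed. The documents give no basis for a frequency, so nothing can be said about how many participants would be affected or harmed. The conclusion also rests on the cited guideline, which could not be reviewed, not supplying the rule. This is a cheap improvement to make at the next amendment; it does not invalidate the liver monitoring.

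**What to change.** In the Table 16-2 row with TBL > 2 × ULN (or INR > 1.5), change the enzyme limits to: *ALT or AST > 3 × ULN if normal at baseline; ALT or AST > 2 × baseline or > 300 U/L, whichever occurs first, if elevated at baseline*. Change the row heading and the column header for that row to ALT or AST. Leave the enzyme-only and symptom rows on ALT.

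This aligns the stop rule with the two combined triggers only. AST > 5 × ULN alone and AST > 3 × ULN with symptoms remain Table 16-1 events without a Table 16-2 row. Like the existing ALT row, the amended row has no ALP or conjugated-bilirubin limit, so it is somewhat wider than the Hy's law definition.

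No new tests are needed: Tables 8-1 and 8-5 already schedule AST, bilirubin and INR, and CK and GLDH are in the Table 16-2 workup. The cost is a rare extra interruption. Under Section 12.4.3, data during a temporary interruption are treated as missing. If no other cause is found, restart is not allowed, the interruption becomes permanent, and all later data for that participant are missing from the primary analysis. One such participant is 1 of 48/2 = 24 (4.2%) in an SjS arm or 1 of 12/2 = 6 (16.7%) in an MCTD arm. The existing ALT row already accepts the same price.

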10.2 Additional Safety Monitoring

10.2.1 Liver safety monitoring

To ensure participant safety and enhance reliability in determining the hepatotoxic potential of an investigational drug, a standardized process for identification, monitoring and evaluation of liver events has to be followed.

Please refer to Section 16.2 for complete definitions of liver laboratory triggers.

Once a participant is exposed to study treatment, every liver event defined in Table 16-1 should be followed up by the investigator or designated personnel at the trial site, as summarized below. Additional details on actions required in case of liver events are outlined in Section 16.2.

- Repeat liver chemistry tests (i.e. ALT, AST, TBL, PT/INR, ALP and G-GT) to confirm elevation. These liver chemistry repeats will be performed using the central laboratory. If results will not be available from the central laboratory, then the repeats can also be performed at a local laboratory to monitor the safety of the participant. If a liver event is subsequently reported, any local liver chemistry tests previously conducted that are associated with this event should have results recorded on the appropriate CRF.
- If the initial elevation is confirmed, close observation of the participant will be initiated, including consideration of treatment interruption if deemed appropriate.
- Discontinuation of the investigational drug (refer to the Discontinuation of study treatment, Section 9.1.1), if appropriate
- Hospitalization of the participant if appropriate

- Causality assessment of the liver event
- Thorough follow-up of the liver event. These investigations can include based on investigator's discretion: serology tests, imaging and pathology assessments, hepatologist's consultancy.
- Obtaining a more detailed history of symptoms and prior or concurrent diseases.
- Obtaining a history of concomitant drug use (including nonprescription medications and herbal and dietary supplement preparations), alcohol use, recreational drug use, and special diets.
- Exclusion of underlying liver disease
- Imaging such as abdominal US, CT or MRI, as appropriate
- Obtaining a history of exposure to environmental chemical agents.
- Considering gastroenterology or hepatology consultations.

All follow-up information and procedures performed must be recorded as appropriate in the eCRF.

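### Table 16-2: the ALT > 8 x ULN row omits participants with raised baseline ALT, so an isolated rise has no mandatory ceiling for two weeks

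*Protocol*

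**What the plan says.** Table 16-2 (Protocol, Appendix 2, Section 16.2) sets actions by ALT level, bilirubin or INR, and symptoms. For an ALT rise with normal bilirubin and no symptoms it has three rows.

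- The lowest row (normal baseline > 3 x ULN; raised baseline > 2 x baseline or > 300 U/L) carries the action "No change to study treatment", followed by "Measure ALT, AST, ALP, GGT, TBIL, INR, albumin, CK, and GLDH in 48-72 hours".
- The middle row leads to interruption. Its raised-baseline limb is "If elevated at baseline: ALT > 3 x baseline or > 300 U/L (whichever occurs first) for more than two weeks".
- The top row is "If normal at baseline: ALT > 8 x ULN", with no duration condition and no limb for a raised baseline.

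Two further rows, for raised bilirubin or INR and for listed symptoms, have limbs for both kinds of baseline and no waiting time.

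Outside the table, Section 10.2.1 says that "every liver event defined in Table 16-1 should be followed up by the investigator or designated personnel at the trial site". For an abnormal baseline, Table 16-1 defines such an event as ALT or AST above 3 x baseline or above 300 U/L.

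**The concern.** The table appears to intend a graded response: watch a modest isolated rise, interrupt a larger one that persists, and interrupt a very large one at once. The last step exists only for participants who start with normal ALT. For those who start high, the lowest row has no upper bound and the middle row needs more than two weeks, so the prescribed action for an isolated rise of any size is to continue drug.

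This is a patient-safety rule for a drug being given for the first time in these two diseases (Protocol Section 3). Section 9.1.1 tells the investigator to follow Section 16.2 when a liver event occurs, so a site that follows the protocol literally is sent to a row that keeps the participant on treatment.

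**Working it through.** No sample size or power figure is involved. The check sets the rows side by side, applies them to a case, and sizes the result.

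**1. The five ALT rows of Table 16-2**

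| Row | Normal baseline | Raised baseline | Other conditions | Action |
|---|---|---|---|---|
| 1 | > 3 x ULN | > 2 x baseline or > 300 U/L | bilirubin normal, no symptoms | continue, repeat tests |
| 2 | > 5 x ULN, over two weeks | > 3 x baseline or > 300 U/L, over two weeks | as row 1 | interrupt |
| 3 | > 8 x ULN | none | as row 1 | interrupt (merged cell) |
| 4 | > 3 x ULN | > 2 x baseline or > 300 U/L | bilirubin > 2 x ULN or INR > 1.5 | interrupt |
| 5 | > 3 x ULN | > 2 x baseline or > 300 U/L | listed symptoms | interrupt |

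Four of five rows have a raised-baseline limb; row 3 does not. The interrupt action for row 3 is read from a cell that seems to span rows 2 to 5. That is the natural reading: a threshold above row 2 with no duration condition serves no purpose unless it interrupts without the wait.

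**2. The rule applied**

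The documents give no ALT ULN. Assume 40 U/L, range 30 to 50.

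- 8 x ULN = 8 x 40 = 320 U/L (8 x 30 = 240 to 8 x 50 = 400).
- The 300 U/L criterion = 300/40 = 7.5 x ULN (300/30 = 10.0 to 300/50 = 6.0).

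Take ALT 410 U/L with normal bilirubin and INR and no symptoms: 410/40 = 10.3 x ULN (410/30 = 13.7 to 410/50 = 8.2).

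- Baseline 28 U/L (normal across the range): above 8 x ULN, so row 3 interrupts at once.
- Baseline 55 U/L (raised across the range): 410/55 = 7.5 x baseline, above 2 x 55 = 110, 3 x 55 = 165 and 300 U/L. Row 1 applies until row 2's two weeks have passed.

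The size of the rise makes no difference. With ULN 40, an ALT of 1,000 U/L (25 x ULN) is interrupted at once from a baseline of 32. From a baseline of 60 or 100 it stays at no change at weeks 0, 1 and 2, and is interrupted only after that. The same pattern appears with ULN set to 30 or 55.

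**3. Worst-case exposure**

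14 days x 2 doses = 28 doses; 28 x 200 mg = 5,600 mg for a participant on MHV370. This holds only if nobody acts on judgement for the whole two weeks.

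**4. What the rest of the protocol mandates**

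- Section 10.2.1: repeat tests; if confirmed, close observation "including consideration of treatment interruption if deemed appropriate"; discontinuation if appropriate.
- Table 16-3, last row ("Any AE potentially indicative of a liver toxicity"): interruption or discontinuation is to be considered.
- Section 9.1.1: discontinuation for laboratory abnormalities or safety risk as the investigator judges, plus a hepatotoxicity guideline that is not in these documents.

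None of these gives an ALT value at which drug must stop.

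**The case against.** The strongest reply is that these participants are not left unwatched. Passing 3 x baseline or 300 U/L is a liver event from the first such value, so Section 10.2.1 applies well before two weeks. At an assumed ULN of 40, that trigger (7.5 x ULN) sits close to the level at which a normal-baseline participant is interrupted. A clinically significant laboratory value is also an adverse event, which can bring in the last row of Table 16-3. This stands: a reader might infer from the no-change wording that nothing happens for two weeks, and the documents do not support that.

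The omission may also be deliberate, since a fixed ULN multiple is less specific in people who start high. Above a baseline of 8/3 = 2.67 x ULN, 8 x ULN falls below 3 x baseline. At ULN 30, a bare 8 x ULN limb would act at 240 U/L, below the table's own 300 U/L criterion. This is a fair point about the form of the fix. It does not explain having no ceiling, because the table already caps its baseline-relative scheme at 300 U/L, whichever comes first.

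The group is narrow as well. Raised bilirubin, INR above 1.5 or a listed symptom (severe fatigue among them) leads to interruption without a wait whatever the baseline. Below 8 x ULN, a normal-baseline participant with an isolated rise also waits two weeks.

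Finally, a reader might infer a series of retests every 48-72 hours across the two weeks. The table states one repeat in that window and gives no frequency, so no count of retests can be drawn from it.

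**Conclusion.** The gap is real but limited. For a participant with raised baseline ALT and an isolated rise, no ALT level in the visible text mandates interruption until the rise has lasted more than two weeks. Surveillance and the investigator's power to stop are in place; the automatic ceiling is not.

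The conclusion rests on reading the merged action cell as covering the > 8 x ULN row, and on the visible text alone. The unseen hepatotoxicity guideline could add a limit. The U/L figures rest on an assumed ULN. The 28 doses are a worst case, not a forecast. The number of participants affected cannot be estimated: much of Section 5.2 is redacted and may contain liver-enzyme limits, and only about 60/2 = 30 participants receive MHV370. It is probably small, although Tables 16-1 and 16-2 clearly provide for abnormal baselines. This is a cheap improvement on patient-safety grounds, not a defect that undermines the trial.

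**What to change.** Add a second limb to the > 8 x ULN row: if elevated at baseline, ALT > 8 x ULN and > 300 U/L. Requiring both keeps the new limit from acting below the table's existing raised-baseline criteria, which never exceed 300 U/L. The effective ceiling would be 320 U/L at ULN 40, 300 at ULN 30 and 400 at ULN 50. Alternatively, use a multiple of baseline with an absolute U/L cap, set by the sponsor's hepatic safety group; this suits participants who start very high better. In either case, state that the no-change row applies only below that limit, and print the interrupt action explicitly beside the row.

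The edit is one limb and one clarifying phrase in an appendix table. The cost is possibly a few more interruptions among participants who start with raised ALT. Table 16-2 allows restart only if another cause is found and enzymes return to baseline, and Section 12.4.3 treats efficacy data during an interruption as missing, so each one may cost some primary-endpoint data. With few participants likely to be affected, that is a reasonable price.
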